9.1 Sample Size

Phase 1 (Dose Escalation)

The sample size for the dose escalation phase is not based on a statistical power calculation. The number of subjects enrolled will be dependent on the DLT incidence. The estimated number of subjects, a minimum of 6 evaluable and up to 18, should provide adequate information for the dose escalation and safety objectives of the study.

Phase 2 (Dose Expansion)

The sample size in phase 2 is up to 104 subjects per dose level. Each dose level may enroll up to 52 R/R AML subjects and up to 52 R/R higher risk MDS subjects. The response rate is monitored using the BOP2 design. For AML, with assumption of the efficacious CRc rate is 30% and the inefficacious CRc rate is 15%, the statistical power would be approximately 0.83 while controlling the type I error rate at 0.10. For MDS, with assumption of the efficacious CR + BM CR + PR rate is 25% and the inefficacious CR + BM CR + PR rate is 12%, the statistical power would be approximately 0.83, while controlling the type I error rate at 0.10.

9.2 Analysis Sets

Detailed criteria for analysis sets will be laid out in classification specifications and the allocation of subjects to analysis sets will be determined prior to database hard-lock.

For each dose level group, the number and percentage of subjects will be characterized for all treated subjects and by each analysis set.

9.2.1 Full Analysis Set

The full analysis set (FAS) will consist of all subjects who are enrolled and receive at least 1 dose of study treatment. This will be the primary analysis set for efficacy analyses.

9.2.2 Response Analysis Set

The response analysis set will consist of all subjects who are enrolled and receive at least 1 dose of study treatment and have at least 1 post baseline primary efficacy measurement. This will be used as a sensitivity analysis set for response related endpoints.

9.2.3 Safety Analysis Set

The safety analysis set (SAF) consists of all subjects who receive at least 1 dose of IP.

The SAF will be used for all summaries of the safety data.

9.2.4 Pharmacokinetic Analysis Set

The pharmacokinetic analysis set (PKAS) consists of the administered population for which pharmacokinetics data are available at least for 1 time point. Additional subjects may be excluded from the PKAS at the discretion of the pharmacokineticist.

9.2.5 Pharmacodynamic Analysis Set

The pharmacodynamic analysis set (PDAS) will include the subjects from the administered population for whom sufficient pharmacodynamic measurements were collected. The PDAS will be used for all analyses of pharmacodynamic data.

9.2.6 DLT Evaluation Analysis Set

The DLT Evaluation Analysis Set (DEAS) is defined as all subjects in SAF by excluding subjects who meet any of the following criteria:

- Subject is discovered to have enrolled without fully satisfying eligibility criteria.
- Subject received less than the planned dose in cycle 1 for reasons other than DLT.
- Subject has no DLT and withdraws from the study before the end of the DLT evaluation period

The DEAS will be used for the analysis of DLT data.

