Upon treatment or post-treatment discontinuation criterion is met and subjects discontinue from the Treatment Period, Observation Period 1, or Observation Period 2, all subjects will be followed for survival and subsequent anti-cancer treatments and outcomes by telephone calls every 3 months.

This study consists of 2 parts: phase 1 dose escalation and phase 2 dose expansion.

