4.1.3 Dose Limiting Toxicity Criteria

A DLT is defined as any of the following events that occur within 28 days starting with the first dose on C1D1 and that is considered to be related to IP. Confirmation of DLTs will be made by the Dose Escalation and Safety Committee (DESC). The severity of AEs will be assessed according to NCI-CTCAE, version 5.0.

DLT is defined as follows:

- Non-hematologic AEs that are \geq grade 3.
- Confirmed Hy's law case.
- New onset of grade 4 thrombocytopenia (with minimum of 2 grade worsening from baseline) within 24 hours of dosing.
- Prolonged myelosuppression, defined as ANC $<$ 500/ μ L for more than 28 days off therapy and in the absence of evidence of active leukemia or MDS in the marrow or blood, will be considered a DLT.

The following AEs will not be considered as DLTs:

- Electrolyte abnormalities that are not associated with clinical sequelae or deemed not clinically significant and corrected with appropriate management or supplementation within 72 hours of onset.
- Grade 3 infusion site reaction if successfully managed and resolved within 72 hours.
- Grade 3 febrile neutropenia with or without infection.
- Alopecia, anorexia or fatigue.
- Grade 3 nausea and/or vomiting if not requiring tube feeding or total parenteral nutrition, or diarrhea and/or constipation if not requiring or prolonging hospitalization that can be

managed to grade \leq 2 with standard antiemetic or antidiarrheal medications used at prescribed doses within 7 days of onset.

- Grade 3 liver function test (LFT) elevations that resolve to \leq grade 1 within 7 days; LFT elevations lasting $>$ 7 days that are considered to be clinically significant and at least possibly related to ASP7517 will be considered to be a DLT.
- Immune-related AEs grade 3 that resolve to \leq grade 1 within 7 days.
- Grade 3 or higher hyperuricemia due to tumor lysis that resolves to \leq grade 1 with medical interventions, including hospitalization with intravenous hydration and/or rasburicase.

Dose evaluation and dose escalation stopping rules based on the BOPIN design with target DLT rate of 0.30 and optimal interval of (0.236, 0.359) are as follows:

Action	Number of Subjects Treated at Current Dose Level					
	3	4	5	6	7	8
Escalate dose if number of subjects with DLT \leq	0	0	1	1	1	1
Stay at current dose level if number of subjects with DLT =	1	1	-	2	2	2
De-escalate if number of subjects with DLT =	2	2	2 or 3	3	3 or 4	3 or 4

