7.3.1 Time Period for Collecting Adverse Event and Serious Adverse Event Information

In order to identify any events that may be associated with study procedures and could lead to a change in the conduct of the study, the sponsor collects AEs even if the subject has not received IP. AE collection will begin from time of informed consent and continue through post-treatment period and at least 30 days after last IP dose and prior to the start of new anticancer treatment. In addition, the following will be collected regardless of the start of new anticancer therapy:

- Any IP-related SAE that is ongoing will be followed until resolved
- Any SAE that is deemed to be related to IP by the investigator

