8.1.1 Discontinuation Criteria from Treatment for Individual Subject(s)

The reason for discontinuation from study treatment must be documented in the subject's medical records.

A subject must discontinue study treatment for any of the following reasons:

- Subject declines further study participation (i.e., withdrawal of consent).

- Any clinical or unacceptable AE/SAE, laboratory abnormality or intercurrent illness, in the opinion of the investigator, indicates continued treatment is not in the best interest of the subject.
- Subject is noncompliant with protocol based on the investigator or medical monitor assessment.
- Subject is found to have significantly deviated from any 1 of the inclusion or exclusion criteria after enrollment (subjects having clinical benefit and no DLT may be kept in the study after discussion with the medical monitor).
- Subject not achieving remission (CRc or PR in AML or CR, BM CR or PR or HI in MDS) and the subject is no longer deriving clinical benefit, in the opinion of the investigator.
- Subject begins other anti-leukemic therapies or MDS therapies, including undergoing HSCT.
- Subject experiences disease relapse/progression.
- Investigator/subinvestigator determines that the continuation of the study treatment will be detrimental to the subject.
- Subject is lost to follow-up despite reasonable efforts by the investigator to locate the subject.
- Female subject becomes pregnant.
- Death.
- Subject develops a grade 4 DLT during cycle 1.
- Delay of > 2 weeks of a subsequent scheduled dose of ASP7517 due to ASP7517-related toxicities.

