8.2 Discontinuation of Individual Subject(s) from Study

All subjects who discontinue study treatment will remain in the study and must continue to be followed for protocol-specific follow-up procedures as outlined in [Section 4.1 Study Design] and the Schedule of Assessments [[Table 1](#), [Table 2](#), [Table 3](#) and [Table 4](#)]. The only exception to this is when the subject specifically withdraws consent for any further contact with him/her or persons previously authorized by the subject to provide this information.

All subjects who discontinue study treatment are to be followed for survival every 3 months after their final visit until death or the final analysis, whichever occurs first per [Section 4.1 Study Design] and the Schedule of Assessments [[Table 1](#), [Table 2](#), [Table 3](#) and [Table 4](#)].

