## **4.6 DLT Evaluation Analysis Set**

The DLT Evaluation Analysis Set (DEAS) is defined as all subjects in SAF by excluding the subjects who meet any of the following criteria:

- Subject is discovered to have enrolled without fully satisfying eligibility criteria.
- Subject received less than the planned dose in cycle 1 for reasons other than DLT.
- Subject has no DLT and withdraws from the study before the end of DLT evaluation period.

The DEAS will be used for the analysis of DLT data.

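### The DLT-evaluable and replacement rules set no minimum follow-up, so a fully dosed subject who dies of leukemia, is lost, or starts new anticancer therapy before day 28 counts as a full DLT-free observation

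*Protocol*

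**What the plan says.** Protocol 9.2.6 defines the DLT Evaluation Analysis Set (DEAS) as the safety set minus three groups: ineligible subjects; "Subject received less than the planned dose in cycle 1 for reasons other than DLT"; and "Subject has no DLT and withdraws from the study before the end of the DLT evaluation period". The replacement rules in the synopsis and 4.1.2 list the same three grounds. SAP 2.2 repeats the replacement list, and SAP 4.6 repeats the analysis-set rule: "Subject has no DLT and withdraws from the study before the end of DLT evaluation period". None of the five places sets a minimum observation time.

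The DLT window (4.1.3) covers IP-related "events that occur within 28 days starting with the first dose on C1D1".

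Leaving treatment is not leaving the study. Under 8.2, "All subjects who discontinue study treatment will remain in the study", and the only exception given there is withdrawal of consent for further contact. Starting other therapy, death, loss to follow-up and "Subject experiences disease relapse/progression" all end treatment under 8.1.1. They also end the observation periods under 8.1.2. After that, by 4.1.1, subjects are "followed for survival and subsequent anti-cancer treatments and outcomes by telephone calls every 3 months".

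Routine AE collection (7.3.1) is to "continue through post-treatment period and at least 30 days after last IP dose and prior to the start of new anticancer treatment". After new therapy starts, 7.3.1 keeps only IP-related SAEs.

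The synopsis and 4.1.2 say a dose level is assessed once the planned number of evaluable subjects have finished the DLT observation period. The synopsis sends the reader to 9.2.6 for the meaning of evaluable.

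**The concern.** A 28-day DLT rate needs each non-event to have been observed for 28 days. The third exclusion is the only one aimed at incomplete follow-up, and it depends on withdrawal from the study rather than on how long the subject was observed. The under-dosing exclusion does not help, because the whole cycle 1 dose is given on day 1. A subject dosed in full who dies of leukemia on day 12, or starts other therapy on day 10, therefore enters the denominator as a complete non-event.

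The ratio of DLTs to DEAS subjects drives escalation, the MTD (10.4.1 and SAP 5.2.2) and the BOIN rule for the China cohort of about 6 (SAP 2.2). Counting part-observed subjects as full non-events can only lower that ratio. Committee review is a limited safeguard: by 10.4.1 the next cohort's dose follows BOIN, and a more conservative choice than the BOIN result is allowed only when setting the RP2D.

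**Working it through.** **1. The plan's own figures.** Target 0.30. I assume the usual BOIN defaults, which the documents do not state: 0.6 × 0.30 = 0.18 and 1.4 × 0.30 = 0.42.

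- Escalation boundary: ln(0.82/0.70) / ln[(0.30 × 0.82)/(0.18 × 0.70)] = 0.1582/0.6691 = 0.2365.
- De-escalation boundary: ln(0.70/0.58) / ln[(0.42 × 0.70)/(0.30 × 0.58)] = 0.1881/0.5245 = 0.3585.

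These agree with the stated interval (0.236, 0.359). The escalate and de-escalate limits in the table for n = 3 to 8 follow from them. The stop limits follow from Pr(rate > 0.30) > 0.95 under an assumed uniform prior. The table itself is sound; the issue is which subjects enter it.

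**2. Who stays in the DEAS.** Take four eligible, fully dosed, DLT-free subjects whose course changes before day 28.

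| Course before day 28 | Withdrawn under 8.2? | In DEAS? | Routine AE collection to day 28? |
|---|---|---|---|
| Withdraws consent for contact | Yes | No | No |
| Dies of leukemia | No | Yes | Ends at death |
| Lost, or starts new anticancer therapy | No | Yes | Ends (related SAEs still collected after new therapy) |
| Progresses, no new therapy | No | Yes | Yes, though scheduled visits may stop |

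Rows two and three are the gap.

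**3. Effect of one such subject, from the protocol table.** Remove one part-observed DLT-free subject and read the action again.

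| As written | Without him |
|---|---|
| 1/5 = 0.200, escalate | 1/4 = 0.250, stay |
| 2/6 = 0.333, stay | 2/5 = 0.400, de-escalate |
| 3/5, de-escalate | 3/4, stop |
| 4/7, de-escalate | 4/6, stop |

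For the MTD, which must not exceed 0.30, 2/7 = 0.286 qualifies and 2/6 = 0.333 does not. This takes the isotonic estimate as the raw rate, with no pooling across doses.

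**4. Illustration only.** Assume a true 28-day DLT rate of 0.40, DLT times uniform over 28 days, follow-up ending on day 14 and every later event missed. A part-observed subject then shows a DLT with probability 0.20.

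- No DLT in three (escalate), all fully observed: 0.6³ = 0.216.
- One of three part-observed: 0.6² × 0.8 = 0.288.
- Two of three part-observed: 0.6 × 0.8² = 0.384.

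For a range, let d be the share of subjects cut short and g the share of their DLTs that go unseen, so the apparent rate is 0.40 × (1 − d × g).

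- d = 10%, g = 0.5: rate 0.38, and 0.62³ = 0.238.
- d = 30%, g = 1: rate 0.28, and 0.72³ = 0.373.
- g near 0 (DLTs all early): the chance returns to 0.216.

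The documents give neither d nor g.

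**The case against.** Four points on the other side have force.

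- **The cohort-review text.** A subject who dies on day 12 has not finished the DLT period, so the synopsis and 4.1.2 could be read as excluding him. But the synopsis defines evaluable by 9.2.6, which has no such condition. The passages conflict and neither one settles the case.
- **Progression.** A reader might infer that progression alone leaves a subject unobserved. The documents do not support that: AE collection runs at least 30 days after the last dose, longer than the 28-day window, unless new therapy starts.
- **Other safety reporting.** Protocol 7.3.3 requires notification of any related AE, serious or not, that the investigator learns of after the collection period. Section 7.3.5 makes every death within 30 days of the last dose an SAE. What can go unseen is therefore narrow: mainly a related, non-serious grade 3 event that never reaches the investigator, or one that would have occurred after the subject died or was lost.
- **Timing and frequency.** Liver and platelet effects in mice appeared one day after dosing, the thrombocytopenia DLT is limited to 24 hours, phase 1 subjects are hospitalized for at least 7 days, and entry requires a life expectancy of at least 12 weeks. Uniform DLT timing is probably pessimistic.

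These points limit the size of the problem. They do not change the rule, which still counts the subject as fully observed.

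**Conclusion.** The gap is real, and it lies in a stated rule rather than in missing detail. It is confined to eligible, fully dosed, DLT-free subjects who die without a DLT, are lost, or start new anticancer therapy before day 28. The direction is towards safe. At these cohort sizes one such subject is enough to change a BOIN action or MTD status, and that follows from the protocol's own table without further assumptions beyond unpooled rates for the MTD.

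Two stronger readings are not supported. One is that the DLT rate is known to be materially understated. The documents give no rate of early loss and no DLT timing, so the rise from 0.216 to 0.288 is an illustration and the true effect may be small. The other is that the phase 2 stopping model is biased by a known amount. It uses all DLT data, and 9.2.6 names the DEAS as the set for DLT analysis, but neither document states the model's denominator or prior. An effect there is a reasonable inference that cannot be sized.

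**What to change.** In the protocol synopsis, 4.1.2 and 9.2.6, and in SAP 2.2 and 4.6, reword the third criterion to: *Subject has no DLT and was not observed for AEs through the end of the 28-day DLT evaluation period, for any reason.* Reconcile the cohort-review sentence in the synopsis and 4.1.2 with it, so that evaluable has one meaning. State that the phase 2 safety model and the China cohort use the same denominator. No change to the AE collection period is needed, since a subject whose collection ends early is simply non-evaluable.

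Dropping only DLT-free part-observed subjects gives a modest upward, conservative bias, because part-observed subjects with a DLT are kept. For example, take a true rate of 0.40 with 25% of subjects seen for half the window, under the timing assumptions above. Observed DLTs are 0.75 × 0.40 + 0.25 × 0.20 = 0.35, the denominator is 1 − 0.25 × 0.80 = 0.80, and the apparent rate is 0.35/0.80 = 0.4375. So add a sensitivity summary that keeps the part-observed subjects.

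The cost is one reworded criterion and possibly a few more replacements. These must fit both the maximum of 8 per dose level and the approximately 18 planned for phase 1, which three levels of six already use (3 × 6 = 18). The staggered enrollment would add some time.

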9.3 Demographics and Baseline Characteristics

9.3.1 Demographics

Demographics and baseline characteristics will be summarized by dose level and overall for all treated subjects.

9.3.2 Subject Disposition

The number and percentage of subjects who completed and discontinued treatment and reasons for treatment discontinuation will be presented for all enrolled subjects by dose level group and overall. Similar tables for screening disposition, observation period disposition and follow-up disposition will also be presented for all treated subjects by dose level and overall. All disposition details and dates of first and last evaluations for each subject will be listed.

9.3.3 Previous and Concomitant Treatment (Medication and Nonmedication Therapy)

All previous and concomitant treatment will be listed. The frequency of previous and concomitant medications (prescription, over-the-counter, and nutritional supplements) will be summarized by dose level and overall.

9.3.4 Medical History

Medical history for each subject will be listed.

9.3.5 Investigational Product Exposure

The number and percentage of subjects exposed to IP will be summarized by dose level and cycle.

All IP exposure data will be listed.

9.4 Analysis of Efficacy

Efficacy analysis will be conducted on the FAS. The interpretation of results from statistical tests will be based on the FAS.

9.4.1 Analysis of Primary Endpoint

9.4.1.1 Primary Analysis

CRc rate is defined for AML subjects as the number of subjects who achieve the best response of CRc (CR, CRp or CRi) divided by the number of subjects in the analysis population.

Response to treatment will be defined per modified Cheson criteria [Cheson et al, 2003].

CR + BM CR + PR rate is defined for MDS subjects as the number of subjects who achieve the best response of CR + BM CR + PR divided by the number of subjects in the analysis population. Response to treatment will be defined per Cheson criteria [Cheson et al, 2006].

Response rates will be calculated and its 90% confidence interval will be constructed by Clopper-Pearson method by dose level for phase 1 and by dose level and disease type for phase 2.

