- If the posterior mean of the safety event rate is higher than 30% as indicated by Bayesian logistic model across disease types at a given dose level, then enrollment will be stopped in phase 2 at that dose level and at higher dose levels for that therapy.
- Additionally, if the posterior mean of the safety event rate is higher than 30% as indicated by Bayesian logistic model in a specific disease type at a dose level, enrollment of that dose level and any higher dose-level will be stopped for that disease type.

Statistical Methods

Sample Size Justification:

Phase 1 (Dose Escalation): The sample size for the dose escalation phase is not based on a statistical power calculation. The number of subjects enrolled will be dependent on the DLT incidence. The estimated number of subjects, a minimum of 6 evaluable and up to 18, should provide adequate information for the dose escalation and safety objectives of the study.

Phase 2 (Dose Expansion): The sample size in phase 2 is up to 104 subjects per dose level. Each dose level may enroll up to 52 R/R AML subjects and up to 52 R/R higher risk MDS subjects. The response rate is monitored using the BOP2 design. For AML, with assumption of the efficacious CRc rate is 30% and the inefficacious CRc rate is 15%, the statistical power would be approximately 0.83 while controlling the type I error rate at 0.10. For MDS, with assumption of the efficacious CR + BM CR + PR rate is 25% and the inefficacious CR + BM CR + PR rate is 12%, the statistical power would be approximately 0.83, while controlling the type I error rate at 0.10.

Efficacy:

For R/R AML: Response to treatment will be defined per modified Cheson criteria [Cheson et al, 2003].

For R/R higher risk MDS: Response to treatment will be defined per Cheson criteria [Cheson et al, 2006].

Response rates will be summarized using exact 90% confidence interval by dose level for phase 1 and by dose level and disease type for phase 2. Time to endpoints, including event free survival and overall survival, will be listed and summarized using Kaplan-Meier method.

Pharmacokinetics:

Summary statistics of pharmacokinetics may be tabulated. Exploratory analysis between pharmacokinetic parameter and clinical measures (e.g., efficacy or safety) may be performed.

Pharmacodynamics:

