9.4.1.3 Phase 2 Expansion

The CRc rate for subjects with R/R AML and CR + BM CR + PR rate for R/R higher risk MDS are continuously monitored using the BOP2 design [Zhou et al, 2017]. The number of dose levels investigated during phase 2 will be based upon the data from phase 1. Initially, 12 subjects will be enrolled at each dose level for each disease type during stage 1 of BOP2. If the response rate does not meet the optimal stopping boundaries (see table below), then stage 2 will open and an additional 20 subjects may be enrolled during this stage. Combining the data from stage 1 and stage 2, stage 3 may be opened for an additional 20 subjects for a total maximum sample size of 52 for each disease type, if the response rate does not meet the optimal stopping boundaries (see table below). Otherwise, the enrollment at that dose level will be closed.

When the total number of subjects reaches the maximum sample size of 52, it may be concluded that ASP7517 is efficacious if the number of responses is greater than or equal to 12 and 10 for AML and MDS, respectively. The number of subjects in stage 1, stage 2 and stage 3 may be changed according to the optimized stopping boundaries.

Optimized Stopping Boundaries for AML	
Number of subjects treated	Stop if number of responses ≤
12	1
32	5

AML: acute myeloid leukemia

Optimized Stopping Boundaries for MDS	
Number of subjects treated	Stop if number of responses ≤
12	0
32	4

MDS: myelodysplastic syndrome

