### 6.4.1 Analysis of Primary Efficacy Endpoints

For Phase 2, the primary efficacy endpoint will be CRc rate for subjects with R/R AML and (CR+ BM CR +PR) rate for subjects with R/R higher risk MDS.

- AML
  - CRc rate is defined for AML subjects as the number of subjects who achieve the best response of CRc (CR, CRp or CRi) divided by the number of subjects in the analysis population.
  - Response to treatment will be defined per Cheson et al., 2003
  - Response rates will be calculated and their 2-sided 90% confidence intervals will be constructed by Clopper-Pearson method by dose level for phase 1 and by dose level and disease type for phase 2.
- MDS
  - CR + BM CR + PR rate is defined for MDS subjects as the number of subjects who achieve the best response of CR or BM CR plus the number of subjects who achieve the best response of PR divided by the number of subjects in the analysis population.
  - Response to treatment will be defined per Cheson et al., 2006
  - Response rates will be calculated and their 90% confidence interval will be constructed by Clopper-Pearson method by dose level for phase 1 and by dose level and disease type for phase 2.

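### The phase 2 primary response rates get a fixed-sample 90% Clopper-Pearson interval although cohort size depends on the responses, so the 90% level is not guaranteed and falls locally to 87.5%

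*Protocol*

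**What the plan says.** The primary estimate is a raw proportion. For AML it is the number of subjects who "achieve the best response of CRc (CR, CRp or CRi) divided by the number of subjects in the analysis population" (protocol 9.4.1.1); the MDS rate is built the same way.

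The interval is stated three times: protocol 9.4.1.1 ("Response rates will be calculated and its 90% confidence interval will be constructed by Clopper-Pearson method"), the synopsis ("Response rates will be summarized using exact 90% confidence interval") and SAP 6.4.1 ("Response rates will be calculated and their 2-sided 90% confidence intervals will be constructed by Clopper-Pearson method"). In phase 2 it is given by dose level and disease type.

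Protocol 9.4.1.3 makes the size of each of those cohorts depend on its responses. Twelve subjects enter stage 1, and 20 more follow if the futility boundary is not met. After that, "Combining the data from stage 1 and stage 2, stage 3 may be opened for an additional 20 subjects", for a maximum of 52. The protocol boundaries are 1/12 and 5/32 for AML, and 0/12 and 4/32 for MDS. SAP 6.7 gives 6/32 for AML.

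Neither document adjusts the estimate or the interval for these looks. Protocol 9.4.1.2 defers sensitivity analyses to the SAP. SAP 6.4 offers the response analysis set and investigator-reported response, and neither addresses the stopping.

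**The concern.** Clopper-Pearson puts at most 5% in each tail for one fixed n. Here a low result can occur at any of three sample sizes. The outcomes whose upper limit lies below the truth are collected separately at 12, 32 and 52, and their probabilities add. The total can exceed 5% even though no single look does. Futility-only stopping also freezes low results at small n, which pulls the average of x/n below the true rate.

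This is the primary efficacy readout of phase 2. A reader who takes the synopsis at its word will treat 90% as a guaranteed level and the upper limit as a 5% error bound.

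**Working it through.** **Inputs.** Stage sizes 12, +20, +20; boundaries b1, b2 of 1, 5 (AML) and 0, 4 (MDS); success at 12 or more of 52 (AML) and 10 or more of 52 (MDS), all from protocol 9.4.1.3. Design rates 15% against 30% (AML) and 12% against 25% (MDS), power about 0.83 and type I error 0.10, from protocol 9.1.

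**1. Outcome probabilities.** With Bin(x; n, p) the binomial probability:

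- P(12, x) = Bin(x; 12, p), for x ≤ b1
- P(32, x) = Σ over a > b1 of Bin(a; 12, p)·Bin(x−a; 20, p), for b1 < x ≤ b2
- P(52, x) = Σ over a > b1 and a+b > b2 of Bin(a; 12, p)·Bin(b; 20, p)·Bin(x−a−b; 20, p)

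**2. The plan's own figures.** P(n = 52 and x ≥ 12) is 0.829 at 30% and 0.067 at 15% (AML). P(n = 52 and x ≥ 10) is 0.835 at 25% and 0.078 at 12% (MDS). These agree with power of about 0.83 and type I error within 0.10, so the model is the planned design.

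**3. Coverage of the planned interval.** The limits are L = Beta⁻¹(0.05; x, n−x+1) and U = Beta⁻¹(0.95; x+1, n−x). Coverage at p is the sum of P(n, x) over outcomes with L ≤ p ≤ U.

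| Cohort | True rate | U below truth | L above truth | Coverage |
|---|---|---|---|---|
| MDS | 12% | 0.0% | 3.9% | 96.1% |
| MDS | 25% | 6.0% | 4.3% | 89.7% |
| MDS | 26.4% | 8.7% | 3.8% | 87.5% (minimum) |
| AML | 15% | 0.0% | 3.5% | 96.5% |
| AML | 30% | 3.1% | 4.0% | 92.9% |
| AML | 33.9% | 7.9% | 4.5% | 87.6% (minimum) |

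The upper limit misses most often at 8.8% (MDS) and 8.7% (AML), against a nominal 5%. MDS coverage is below 90% in patches between about 22.5% and 30.6%. AML coverage is at least 90.3% throughout 15% to 30%. Over true rates from 5% to 40%, about 12% (AML) and 13% (MDS) of the grid is below 90%.

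The MDS minimum shows the mechanism. The upper limits for 0/12, 4/32 and 8/52 are 22.1%, 26.36% and 26.05%, all below 26.4%. The chance of 0/12 is 0.736¹² = 2.5%, stopping at 32 has 4.0%, and 5 to 8 of 52 has 8.7 − 2.5 − 4.0 = 2.2%. Each is under 5%; the sum is 8.7%.

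**4. Bias of x/n.** E(x/n) = Σ P(n, x)·x/n. For AML at 15%, stops at 12 contribute 0.15·0.85¹¹ = 0.0251, stops at 32 contribute 0.0355, and cohorts reaching 52 contribute 0.285 × 0.1948 = 0.0555. The sum is 0.116, or 11.6%. For MDS at 12% the mean is 9.6%. At the design alternatives the bias is −1.7 points (AML, 30%) and −0.9 points (MDS, 25%). Among cohorts that reach 52 the sign reverses: the mean is 30.8% at 30% (AML) and 25.7% at 25% (MDS).

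**5. The adjusted interval.** Order outcomes by final n, then by x. The lower limit solves P(this outcome or higher) = 0.05; the upper limit solves P(this outcome or lower) = 0.05. Minimum coverage becomes 90.0% (AML) and 90.3% (MDS). The UMVUE is the share of admissible response sequences ending at (n, x) in which a given stage 1 subject responds; its mean equals the true rate.

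| Result | Raw rate, planned interval | UMVUE, stage-wise interval |
|---|---|---|
| AML 1/12 | 8.3%, 0.4–33.9% | 8.3%, 0.4–33.9% |
| AML 5/32 | 15.6%, 6.4–30.1% | 20.8%, 7.1–35.0% |
| AML 12/52 | 23.1%, 13.9–34.7% | 26.6%, 14.3–37.2% |
| AML 18/52 | 34.6%, 23.7–46.9% | 35.4%, 23.8–47.1% |
| MDS 10/52 | 19.2%, 10.8–30.4% | 21.1%, 11.1–31.3% |

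**6. The SAP's AML boundary.** With 6 instead of 5 at 32 subjects, minimum AML coverage of the planned interval is 86.0% and power is 0.801.

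**The case against.** The strongest reply is that little turns on this. Efficacy and futility are decided from counts, so no decision uses the interval. The worst shortfall is 2.5 points, it is 0.3 points at the MDS design alternative, and mean coverage over 5% to 40% is about 94%. All of that stands, and it limits the weight of the point.

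Three stronger readings are tempting, and the documents do not support them.

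- *The planned interval rules out the 30% AML target too firmly.* A cohort stopped at 3/32 gets 2.6–22.5% as planned and 4.0–33.9% stage-wise, which seems to show this. But when the true AML rate is 30%, the planned upper limit falls below 30% only 3.1% of the time, under the nominal 5%. The gap in the example reflects the ordering, which gives 1/12, 2/32 and 3/32 almost the same upper limit. For MDS stopped at 32, no result has the planned interval excluding 25% while the stage-wise interval includes it.
- *Every stopped cohort has an upper limit that is too low.* Cohorts stopped at 12 get the same interval under both methods, and for AML at 15% that is the commoner stop (44%, against 27% at 32).
- *The reported rate is biased downward.* That is true only on average over all stopping outcomes. Cohorts that reach 52 are the only ones that can be declared efficacious, and their bias is upward.

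Preferring the UMVUE as the headline estimate would also be a bias-variance choice. For AML at 15% its root mean squared error is 0.090, against 0.076 for the raw rate.

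**Conclusion.** The point holds in a limited form. The interval labelled exact does not guarantee 90% coverage under this design. The shortfall is local and falls on the upper limit: minimum 87.5% (MDS) and 87.6% (AML), with upper-limit misses up to about 8.8%. It matters most for MDS, where the affected rates surround the 25% target. The raw rate is too low on average and too high given that the cohort reaches 52. The fault lies in the reported estimate and its error bars; the decision rule and its error rates are sound.

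The figures assume the protocol boundaries, binding stops, and looks at exactly 12 and 32 subjects. Overrun, or a change of stage sizes, which protocol 9.4.1.3 permits, would change them, as would the SAP's AML boundary.

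**What to change.** 1. Reconcile the AML boundary at 32 subjects between protocol 9.4.1.3 (5) and SAP 6.7 (6). The adjusted interval cannot be computed until this is settled.
2. In protocol 9.4.1.1 and SAP 6.4.1, for the phase 2 primary rates, pre-specify a 90% interval that inverts the exact three-stage distribution under stage-wise ordering, using the boundaries and look sizes actually applied. Amend the synopsis wording to match.
3. Keep x/n as the displayed rate and show the UMVUE beside it as a supplementary estimate.
4. Keep Clopper-Pearson for phase 1 and for endpoints that do not drive stopping.

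The cost is SAP and protocol wording and a short program, with no added subjects and no change to any go/stop decision. The price is wider intervals for cohorts stopped at 32 and for low counts at 52, and the larger error of the UMVUE at low rates, which is why it should stay supplementary.
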